#### Labelling of AEs and SAEs.

Severity. AEs and SAEs will be labelled according to severity by one or both of the PIs, based on their impact on the patient. An AE will be termed "mild" if it does not have a major impact on the patient, "moderate" if it causes the patient some minor inconvenience, and "severe" if it causes a substantial disruption to the patient's well-being.

*Relatedness.* AEs will also be categorized according to the likelihood that they are related to participating in the study. Specifically, they will be labelled “definitely unrelated”, “possibly related”, “probably related”, or “definitely related”.

#### **6.1.7 Protocol violations**

Study staff will inform the Principal Investigators (PI) as soon as they are aware of any violations to the protocol. The South African PI will report any violations and the corrective actions taken to prevent further violations within 7 days to the SAMRC ethics committee.

#### **6.1.8 Adverse events and unanticipated problems**

As this study consists of low-risk meetings with a PRC, we do not anticipate having any study-related AEs, SAEs, or unanticipated problems. However, given that many participants in this study are from a vulnerable population (i.e., PLWH and SUD who have fallen out of HIV care), and are enrolled for about six-months, it is possible that AEs, SAEs, and unanticipated problems will arise. The plan for monitoring and reporting AEs, SAEs, and unanticipated problems is below.

**Monitoring.** At follow-up assessments, study staff will ask participants if they experienced any AEs or SAEs since the last assessment (e.g., hospitalizations). The PRC(s) will also be trained to let the study team know if they are aware of any AEs or SAEs.

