#### **Rationale for Enrolment Numbers.**

As this is a pilot study with the primary goal of establishing feasibility and acceptability, we view our effectiveness effect size as preliminary. However, based on prior work in this population and with PRCs, we expect to find a small improvement in patient re-engagement in care in enhanced treatment as usual (ETAU; previous studies have found about 14% re-engagement in ETAU) and a larger improvement in the PRC condition (previous studies have found 66-89% improvement). Assuming ETAU re-engages at an even higher rate (i.e., 24%), and Siyakhana (PRC condition) re-engages at the low end of previous studies (i.e., 66%), enrolling 50 patients will give us approximately 85% power to detect a difference in patient re-engagement after accounting for up to 20% attrition and/or missing records.

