#### ETAU Training (Psychoeducation):

Both COPC teams will receive the ETAU training from our study team. This training will consist of psychoeducation around how to screen and refer for SU in HIV patients, the prevalence of SU in HIV, and the impact SU has on HIV care. This training will last for 1-2 days, depending on COPC availability. A brief psychoeducation refresher course (i.e., one afternoon a week or two after the original training) will also be offered. The purpose of this refresher will be to review how to screen and refer patients for substance use and answer any questions about screening and referring.

**PRC Integration Training:** Only the COPC randomized to the Siyakhana (PRC+ETAU) condition will receive the Siyakhana PRC Integration Training. In this training, the already trained PRC will be introduced to HCWs in the Siyakhana COPC. Together, the PRC and these HCWs will be trained on the PRC role (i.e., the difference between a PRC and a CHW) and how to refer to the PRC. This

Figure 1. HCW Procedures

training will last from 1-2 days, depending on COPC availability. After the training, the PRC will join this COPC (e.g., shadow team members before patients are enrolled, work closely with the COPC team, attend weekly COPC supervision) for the remainder of the study.

**Active Treatment Phase:** After the training(s), HCWs in both COPCs will continue visiting and treating patients as usual. The treatment as usual will potentially be enhanced (i.e., ETAU) by HCWs now being trained in how to screen patients for SU, and how to refer patients to local, publicly-funded SU treatment programs. The study team will provide each COPC with initial SU screeners, and let the COPCs know that the team can provide more screeners at any time during the active phase of the study.

**Siyakhana:** HCWs in the Siyakhana COPC will be aware that any patients who enroll in the study will be invited to meet with the PRC. This PRC will be present at COPC meetings, supervisions, etc.

**HCW 3MFU:** Approximately three-months after the PRC integration (i.e., enrollment of first patient participant), all HCW participants will be asked to complete a three-month follow-up (3MFU) assessment. This brief assessment will consist of the same self-report stigma measures as the HCW baseline assessment.

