### 3.1.2 COPC Patients: Procedures

Study procedures for patient participants in the Pilot PRC Study are described below and illustrated in Figure 2.

**Patient Screening & Enrolment.** At least once a week, the study team will consult with enrolled COPC HCWs on patients who may be interested in participating in the study. The study team will contact these patients and briefly tell them about the study. If a patient is still interested in potentially participating, the study members will officially screen the patient. If the patient is still interested in participating after screening and met all eligibility criteria, a staff member will complete the informed consent process with the patient as soon as possible. The consent form will include all study procedures and state that we are seeking approval to extract information from medical records (i.e., information related to clinic visits (dates, attendance), HIV (viral load, CD4 count), care for other chronic diseases, referrals to other programs including SU treatment programs, etc.). It will also state that we are seeking approval to see if they attended local publicly funded SU treatment programs (date(s) of attendance, location(s) attended), provided through the South African Community Epidemiology Network on Drug Use (SACENDU). Finally, it will state that the study will only collect medical record and SU treatment program attendance data between the date of their baseline assessment and the date of 6MFU.

**Patient Baseline Assessment:** Upon completing informed consent, all patients will be asked to complete a self-report baseline assessment with a study team member. Ideally the baseline assessment will be completed immediately after informed consent is given. However, if the patient is unable to complete the baseline assessment immediately after consent, a time to complete the assessment will be scheduled for as soon as possible. The patient baseline assessment consists of self-report questions around demographics, SU, HIV, and stigma. After the baseline assessment, all patient participants will be given another referral to the nearest free SUD treatment program(s) (for example, the Help Me Network).

[figure not shown]
**Patient Active Treatment Phase: 0 to 12 weeks post-baseline.** Following the completion of the patient baseline assessment, the below procedures will occur.

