**ETAU Patients.** Patients seen by the ETAU COPC will continue to receive normal treatment from their COPC HCWs (i.e., normal efforts to re-engage patients in HIV care). These normal visits will be enhanced through (1) their COPC HCWs knowing how to, and therefore, potentially screening them for problem SU, and (2) their COPC HCWs knowing how to give referrals to local SU treatment programs. It is also possible that they will receive enhanced care from their COPC HCWs due to their COPC HCWs now knowing more about SU in the context of HIV.

**Siyakhana (PRC+ETAU) Patients.** Patients seen by the Siyakhana COPC will be invited to attend sessions with a PRC after their baseline assessment.

The structure and content of PRC sessions were designed based on patient and stakeholder feedback about PRCs (Protocol IDs: EC049-11/2021, EC046-10/2020). Siyakhana patient participants will be invited to meet with the PRC on a regular basis for approximately 12-weeks (3-months). Each meeting will be scheduled to last approximately 30 minutes, although an hour will be allocated for each meeting. The PRC and patient together will decide where to meet in a venue that is physically and psychologically safe for both the PRC and patient. Options deemed safe by stakeholders and patient participants in our formative work included the library, the local clinic, community centers, and for some, their homes. The location that the PRC and patient chooses will be recorded so that we have this information for future iterations of this project. The goal of these meetings will be for the PRC to motivate the patient to return to HIV care and seek SUD treatment. In training the PRC, the PRC will have attained competence in providing brief education around SU and HIV, supporting the patient in their recovery, and helping the patient problem-solve barriers to accessing both HIV and SU care.

Figure 2. Patient Procedures

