#### **Reporting to SAMRC HREC.**

*AEs.* If any AEs occur, they will be reported to the SAMRC HREC during the yearly progress report.

*SAEs.* All SAEs will be reported to the SAMRC HREC within 48 hours of the team discovering the SAE, regardless of whether or not it is related to the study.

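### The only named between-visit route for AEs and SAEs is the PRC, who works in one arm, so ETAU events may be discovered about 12 weeks late and ETAU deaths have no named route

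*Combined protocol and SAP*

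**What the plan says.** The Monitoring paragraph of section 6.1.8 gives two sources of AE and SAE information.

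- **Both arms:** "At follow-up assessments, study staff will ask participants if they experienced any AEs or SAEs since the last assessment (e.g., hospitalizations"). Section 3.1.2 (COPC Patients: Procedures) sets the patient follow-ups at about 3 and 6 months after baseline.
- **Through the PRC:** "The PRC(s) will also be trained to let the study team know if they are aware of any AEs or SAEs".

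The PRC is part of one team only. In section 3.1.1 (COPC HCWs: Procedures), "Only the COPC randomized to the Siyakhana (PRC+ETAU) condition will receive the Siyakhana PRC Integration Training", and "After the training, the PRC will join this COPC". For the other arm, section 3.1.2 says that "Patients seen by the ETAU COPC will continue to receive normal treatment from their COPC HCWs". The training given to both teams covers substance-use screening, referral, prevalence and impact on HIV care. It does not mention reporting adverse events.

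Under Reporting to SAMRC HREC, every SAE, related or not, is to be reported "within 48 hours of the team discovering the SAE".

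Two other contacts reach both arms between visits. Section 3.1.2 says "At least once a week, the study team will consult with enrolled COPC HCWs", but the stated subject is possible recruits. Section 4.1.2 has medical records monitored throughout the study, with clinic attendance as the item extracted. Neither is described as a source of safety information.

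**The concern.** The extra reporter is part of the intervention, so the two arms are watched unequally. During the session phase the PRC sees Siyakhana patients every week or two. Nobody is given the same task for ETAU patients, who must wait for the next assessment.

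The visit question also depends on the patient being there to answer it. A patient who has died cannot report it, and the plan names no informant or mortality check. A patient who misses the 3-month visit can be asked only at 6 months. One who misses both is never asked.

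The 48-hour limit does not help, because it starts at discovery. The team could meet it in full while an ETAU hospitalisation stayed unknown for weeks. The protocol itself describes many participants as vulnerable, accepts that SAEs may occur, and requires all of them to be reported, so ETAU events matter as much as Siyakhana events.

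**Working it through.** The plan states no detection lag, so there is no figure to reproduce. The lag follows from the visit and session schedule.

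**Inputs**
- Follow-up assessments at weeks 12 and 24 in both arms (section 3.1.2, taking 3 months as 12 weeks).
- PRC sessions from the flexible guideline table in section 3.1.2: one in week 1, weekly in weeks 2–4, every other week in weeks 5–8, as needed in weeks 9–12, optional boosters afterwards. I place them at weeks 1, 2, 3, 4, 6 and 8, and try two cases for weeks 9–12: no session, or one every two weeks.
- Assumptions: events fall uniformly over time, the patient attends, and the event is found at the next scheduled contact.

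**Formula.** With gaps g between contacts over T weeks, the longest lag is the largest g and the mean lag is Σg² / (2T).

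**Results**
- ETAU, weeks 0–12: one gap of 12. Maximum 12; mean 144/24 = 6.0 weeks.
- ETAU, weeks 0–24: two gaps of 12. Maximum 12; mean 288/48 = 6.0 weeks.
- Siyakhana, weeks 0–12, no session in weeks 9–12: gaps 1, 1, 1, 1, 2, 2, 4. Maximum 4; mean 28/24 = 1.17 weeks.
- Siyakhana, weeks 0–12, a session every two weeks in weeks 9–12: gaps 1, 1, 1, 1, 2, 2, 2, 2. Maximum 2; mean 20/24 = 0.83 weeks.
- Siyakhana, weeks 12–24, no boosters: one gap of 12. Maximum 12; mean 6.0 weeks, the same as ETAU.
- Siyakhana, weeks 0–24, no boosters: mean (28 + 144)/48 = 3.58 or (20 + 144)/48 = 3.42 weeks.

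The gap in timing therefore lies in the first 12 weeks. Over the full 24 weeks the means are about 3.4–3.6 against 6 weeks.

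**Completeness of non-fatal events.** Let m be the share of patients with events who never attend a follow-up, and q the share of those missed events that the PRC hears of. Visit questioning finds 1 − m in ETAU, and Siyakhana finds 1 − m(1 − q). Neither m nor q is in the documents. With q assumed to be 0.5:
- m = 0: 100% in ETAU, 100% in Siyakhana.
- m = 0.10: 90% in ETAU, 95% in Siyakhana.
- m = 0.20: 80% in ETAU, 90% in Siyakhana.

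Apart from poor recall at visits, final counts differ only to the extent that patients are never assessed. Deaths are different: the visit question finds none of them.

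**The case against.** The case on the other side has real force.

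- **No safety comparison is planned.** Neither the objectives in section 1.2 nor the analyses in section 4 include an AE or SAE outcome. A reader might infer that a planned safety comparison is biased. The documents contain no such comparison, so the bias could affect only a descriptive or later one.
- **The visit question is the same in both arms.** It looks back to the last assessment and may be asked by phone. For non-fatal events recalled at attended visits, the arms differ in timing and not in the final count. This stands.
- **Section 6.1.8 does not say that its two routes are the only ones.** An SAE that came up in a weekly consultation or in the records would still be reportable. That is true, but it would be found by chance, because neither contact is assigned to safety.
- **PRC contact is uneven.** Sessions are by invitation, flexible, and can be paused for a month. The Siyakhana lags above are guideline values for patients who attend.
- **The risk is low, and more vigilance where the new contact takes place is defensible.** That explains why the PRC reports. It does not explain why ETAU has no counterpart when all SAEs must be reported regardless of relatedness.

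A reader might also take the allowance in the patient sample-size rationale, "after accounting for up to 20% attrition and/or missing records", to mean that 5 of 25 ETAU patients (20%) have no route, and that Siyakhana would show 1/0.8 = 1.25 times as many events. Neither follows. The 20% is a planning margin for the re-engagement analysis that mixes dropout with missing records. It is not a rate of unanswered safety questions. The ratio also requires the PRC to hear of every event in patients who have stopped attending assessments.

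**Conclusion.** The gap is real but narrower than it first looks. As written, the plan lets an ETAU event go undiscovered for up to about 12 weeks, 6 on average, against an average of about 0.8–1.2 weeks in Siyakhana during the session phase. After week 12 the arms are similar unless boosters are used. These figures assume uniform events, discovery at the next scheduled contact, attendance, and PRC sessions held as the guideline suggests. Outside the PRC's reach, no named route captures a death or an event in a patient who does not return.

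The main consequence is late or missed SAE reporting that still complies with the 48-hour rule. The second is that AE or SAE counts shown by arm would tend towards more and earlier events in Siyakhana even if true rates were equal. The documents give no basis for putting a size on that second effect. A reader might also infer that PRC reports wait for the weekly or biweekly supervision before the 48 hours begin. The plan does not say so; stating when the clock starts would be a clarification only. The HCW stigma outcome is not affected.

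**What to change.** Amend section 6.1.8 as follows.

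1. Add a check for deaths, hospitalisations and other SAEs to the medical-record monitoring already done in both arms, including for patients who miss the 3- or 6-month assessment, and state how often it is done. If an event is in the records, a check every r weeks gives a lag of at most r and a mean of r/2. If needed, name admissions and deaths among the record items in the consent form, whose present list does not mention them.
2. While the weekly consultation with health workers of both teams is running, add one question on SAEs or deaths among enrolled patients. If it is held exactly weekly and the health worker knows of the event, the lag is at most 1 week and 0.5 week on average in both arms. The consultation is described for recruitment only, so continuing it until the last patient reaches 6 months would be an added task.
3. Record the source of each AE and SAE. If counts are shown by arm, show those from routes common to both arms separately from PRC-only reports.

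The cost is slightly more record review, one question to health workers, one source field in the database and a possible consent amendment. No participant visits are added.

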#### **Reporting to SAMRC HREC.**

*AEs.* If any AEs occur, they will be reported to the SAMRC HREC during the yearly progress report.

*SAEs.* All SAEs will be reported to the SAMRC HREC within 48 hours of the team discovering the SAE, regardless of whether or not it is related to the study.

### **Responsibility**

The Multi-PIs (MPIs) are ultimately responsible for data and safety monitoring. The processes described above ensure that the MPIs will be aware of important study related issues on a regular basis.

### **Disclosure of Any Conflict of Interest**

Each investigator will complete a conflict of interest statement which will be kept on file by the study team. Any new investigators or key study staff will complete these forms, which will be stored and kept on record. At this time, there are no conflicts of interests in this study.

## 7. MANAGEMENT DETAILS

### Management Approach

The present study will be led by the two PIs: [name] and [name].

#### 7.1.1 SAMRC

[name] (MPI) will take primary responsibility for SAMRC ethics protocols, training materials, staff training and management, and quality assurance. She will also oversee data collection.

#### 7.1.2 UMD

[name] will oversee data management and the US based team who will support administrative coordination, oversight on regulatory issues and compliance, and all data management and cleaning.

#### 7.1.3 Both Sites

Dissemination & Implementation. Drs [name] and [name] will work collaboratively on the dissemination of findings. Specifically, each PI will take responsibility for gathering and coordinating resources and ensuring outputs for each area of primary responsibility. Leadership will be shared, as will responsibilities, authority, data, and credit. All final scientific and study implementation decisions will be made collaboratively between PIs, with inputs from the project team.

Communication. The PIs will communicate on a regular basis regarding study implementation and progress by telephone or video, in addition to regular email communication. Depending on travel guidelines (due to COVID-19 or other events), [name], [name], and the US team will travel to Cape Town to support study training and implementation.

Conflict Resolution. All final decisions will be made collaboratively between Drs [name] and [name]. In the case of conflicts, the two PIs will work diligently to resolve any issues and will draw on the expertise and inputs of the Co-Is and study collaborators to reach consensus. In the unlikely case that the two PIs cannot come to a consensus, they will seek out a third-party mediator ([name] at the University of Cape Town) to help resolve this conflict.

### Staff and Scientific Collaboration

[name] (MPI) will have the overall responsibility of ensuring procedural and scientific integrity of the SA-based study operations, including overseeing the team at the SAMRC. This will include supporting training and supervising research staff on study measures and assisting with regulatory requirements.

[name] (M PI) will have the overall responsibility of ensuring the procedural and scientific integrity of the US-based study operations, including data management and oversight. She will lead the team at UMD in coordinating research meetings, maintaining a study timeline, creating reports on study projects, handling ethics committee issues, and ensuring clear communication between all study members.

### Facilities

#### 7.1.4 Field Site

The present study team will be based on the SAMRC premises in Delft. This site has all the privileges of SAMRC office space and is the base for several studies located within the community. Project staff will be housed at this facility.

Please note that due to COVID-19, staff may work remotely. If working remotely, staff will still have access to SAMRC resources.

### **7.1.5 Data Management Site**

Data management will primarily occur in the Global Mental Health and Addiction Program (Director: [name]) at UMD. The office space consists of shared office space, a conference room, individual offices, and locked file storage rooms. Data files will be saved to a secure network running the PI's laboratory.

Please note that due to COVID-19, staff may work remotely. If working remotely, staff will still have access to UMD resources including access to the secure network.

## 8. ADDITIONAL DETAILS

### Research Translation

#### 8.1.1 Manuscripts

We plan to publish the findings of this study in peer-reviewed journals. At a minimum we hope to publish a report of the implementation and preliminary effectiveness findings of this pilot study.

#### 8.1.2 Scientific Conferences.

We plan to present findings from this study at scientific conferences, including Addiction Health Services Research (AHSR) annual meeting, the Dissemination & Implementation Science Annual Conference, and the College of Problems on Drug Dependence (CPDD).

#### 8.1.3 Training Materials.

This study will allow for the final adaptation of our PRC model. If at the end of this future study the approach proves to be effective, feasible, and acceptable, we will offer capacity-building workshops to help the Department of Health scale-up peers and make our initial peer training and supervision available to all who would like it.

